In summary, these data indicate that MDD is characterized by reduced hedonic responses and ability to modulate behavior as a function of positive reinforcers. Functional MRI studies suggest that these deficits may reflect ventral striatal, ACC, and OFC abnormalities. Because positive reinforcers increase the likelihood of behavior (Rescorla & Wagner, 1972), blunted reward responsiveness may lead to reduced motivational drive to pursue pleasurable activities, which may in turn contribute to depressive symptoms. Indeed, reduced hedonic capacity (1) characterizes both currently depressed and remitted depressed individuals (Kasch et al, 2002; Pinto-Meza, 2006); and (2) predicts depressive symptoms (Hundt et al, 2007), time to recovery (McFarland et al, 2006), and poor treatment outcome (Kasch et al., 2002; Spijker et al, 2001). The overarching goal of the proposed research is to investigate mesocorticolimbic dopaminergic pathways within young adult females with a history of CSA between the ages of 5-14 years with (“CSA/MDD group”) and without (“CSA/RES group”) a current diagnosis of major depressive disorder (MDD). To disentangle CSA- vs. MDD-related effects, these groups will be compared to not only healthy controls but also MDD females without a history of CSA. We hypothesize that, relative to healthy control and CSA/RES groups, the CSA/MDD participants will be characterized by (1) reduced reward responsiveness and ventromedial prefrontal cortex activation but cortisol hypersecretion when exposed to an acute psychosocial stress manipulation, (2) reduced dopaminergic transmission, and (3) reduced dopamine transporter binding. These hypotheses will be tested using a novel integration of behavioral, endocrinological, and functional/molecular imaging approaches. Improving our understanding of neurobiological mechanisms associated with different CSA outcomes (specifically MDD and resilience) is of paramount importance in order to (1) identify individuals at risk for psychopathology and maladaptive behavior, (2) prevent revictimization, and (3) develop more targeted therapeutic interventions.

II. SPECIFIC AIMS

a. Objectives and hypotheses

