Specific Aim 3: To investigate stress sensitization of the mesocortical system following CSA. We will use high-density, source localized electrophysiology (EEG), and cortisol assessments to probe cortical activation and stress reactivity during a reward learning paradigm performed under acute stress. Relative to control and CSA/RES subjects, the CSA/MDD group will show decreased ventromedial prefrontal cortex (vmPFC) activation and increased cortisol reactivity following acute stress accompanied by impaired reward learning (**Hypothesis 3a**). Relative to healthy controls, the CSA/RES

group will show increased vmPFC activation but similar reward sensitivity and cortisol reactivity (**Hypothesis 3b**).

Specific Aim 4a: To investigate DAT function from DA neurons derived from directed conversion of skin fibroblasts. We will collect a skin biopsy from a subset of the study sample (20 participants) to analyze human-induced neuronal DA cells. We hypothesize that relative to the healthy group (n = 8), individuals with MDD and a history of CSA (n=8) will show altered/downregulated DA-related phenotype (e.g., DAT downregulation; **Hypothesis 4a**). **Similarly, we hypothesize that the CSA/RES subjects (n=4) will show similar DA-related phenotype as the healthy group.**

Specific Aim 4b: To Investigate relations between DAT function and fMRI, PET, ERP, endocrinological and behavioral markers of anhedonic behavior and stress responsiveness. Across all groups, downregulated DAT function will be associated with decreased ¹¹C altropane binding in striatal regions (PET), lower reward-related striatal responsiveness (fMRI), potentiated stress-induced cortisol responses, and stress-induced anhedonia (**Hypothesis 4b**).

Specific Aim 4c: To provide more conclusive tests of the potential role of DAT and NOC dysfunction in the pathophysiology of depression. Post-mortem tissue will be obtained from the Douglas Bell Canada Brain Bank in Montreal, QC, Canada through our collaborator [name], Professor and Chair, Department of Psychiatry, McGill University. Please see Appendix 2 for more details.

III. SUBJECT SELECTION

Inclusion Criteria:

- Females of all ethnic origins, age between 20 and 45; right-handed (Chapman & Chapman 1987);
- Absence of any psychotropic medications for at least 2 weeks (6 weeks for fluoxetine; 6 months for neuroleptics; 2 weeks for benzodiazepines; 2 weeks for any other antidepressants);

Childhood Sexual Abuse/MDD (CSA/MDD):

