A subset of subjects (20 participants) will be invited to participate in an additional study component involving a skin biopsy (see details below) after they have completed the ERP session. A subset of participants from the healthy group (n=8), CSA/MDD group (n=8), and the CSA/RES group (n=4) will participate. Invitations to participate will be extended to all subjects in the healthy group, CSA/MDD group, and CSA/RES group until recruitment for this additional component is complete. Participation in the additional session will require signing of a separate consent form prior to participation. In order to minimize phenotypic heterogeneity and maximize our ability to detect group differences, we will prioritize the cell conversion for participants based on their performance in a laboratory-based measure of anhedonia, the Probabilistic Reward Task (PRT), administered during the ERP session. Specifically, we will prioritize the subjects in the CSA/MDD group showing the greatest impairments in reward learning (as assessed by the PRT) when tested under stress and the healthy control subjects showing the greatest resistance against stress-induced reduction in reward learning (as assessed by the PRT). For all other subjects that do not meet this criteria (including all subjects in the CSA/RES group), skin samples will be frozen until additional funding is acquired. If any of these subjects refuse to participate, investigators will continue prioritizing subjects showing the next greatest level of impairment or resistance (as assessed by the PRT) until they find 3 subjects in each group. A normative database collected by [name] laboratory will be used to identify participants meeting pre-specified cutoffs with respect to their performance in the PRT during stress.

b. Procedures for obtaining informed consent

After screening and approval for participation, subjects will read and sign an IRB-approved informed consent detailing the general purposes and procedures of the experiment, and any questions they may have will be answered. The subjects of this study must be judged capable of understanding the nature of this study as well as the discomforts and potential benefits. This determination will be made by a

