diurnal cortisol fluctuations. This session will involve an EEG recording while participants perform a probabilistic reward task. This session also involves a stress manipulation, the Maastricht Acute Stress Test (MAST; Smeets et al. 2012), and saliva samples for cortisol analysis.

EEG Recording

The probabilistic reward task used in our prior work (see below) will be administered in conjunction with 128-channel ERP recording; subjects will perform the task twice, once before exposure to an acute stressor and once immediately following the stressor. The 128-channel EEG will be recorded using the Geodesic EGI system in an electrically shielded room.

Probabilistic Reward Task

The probabilistic reward task (PRT) has been successfully used by the PI to assess reward responsiveness (e.g., [name] et al 2005, 2007, 2009b). In each trial, subjects choose which of two difficult-to-differentiate stimuli was presented. Stimuli consist of simple cartoon faces (diameter: 25 mm; eyes: 7 mm) presented in the center of the monitor. At the beginning of the trial, the face has no mouth. After a given delay, either a straight mouth of 11.5 mm (“short mouth”) or 13 mm (“long mouth”) is presented for 100 ms. Subjects are instructed to press an appropriate button to decide whether a long or small mouth had been presented. Unbeknownst to subjects, correct identification of one stimulus (“rich stimulus”) is rewarded three times more frequently (“*Correct! You won 20 cents*”) than the other (“lean”) stimulus. In healthy controls, this reinforcement schedule leads to a response bias (i.e., a preference for the more frequently rewarded stimulus). The degree of response bias toward the more frequently reinforced alternative will be used for operationalizing sensitivity to reward.

To avoid carry-over effects, participants complete the PRT twice in which only the stimuli type will vary. In the second version, instead of determining the length of the mouth, participants will need to decide whether a long or short ‘nose’ had been presented on the cartoon face by pressing the appropriate button. All other task parameters remain identical.

One version of the PRT is completed prior to the ‘stress manipulation’ (see below) and the other is completed after the ‘stress manipulation’. The order of the two versions (mouth vs. nose) will be counterbalanced across subjects.

Maastricht Acute Stress Test (MAST)

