Procedure: Because the pharmacokinetics of amisulpride are linear and similar across gender, and a first peak plasma concentration is seen 1-1.5 hr after oral administration (Ascalone et al, 1996), fMRI scanning will start 1 hr after administration of amisulpride (or placebo). During the one-hour wait between the administration of amisulpride (or placebo), participants may read or view a neutral film. During this time, experimenters will carefully monitor participants to assess the presence/absence of side effects. A designated study physician will be present at the neuroimaging facility throughout the session with a response time of 2-3 minutes in case study participants experience adverse side effects during the fMRI scanning. After one hour, participants will be asked to enter the scanner, and data collection will begin. The dose (50 mg) was selected based on prior studies (Hamon-Vilcot et al., 1998; Samuels et al, 2006), and the observation that all prior studies using amisulpride in depressive disorders have used 50 mg/day doses (see above). Using a double-blind design, half of the participants in each group will be administered amisulpride, whereas the other half will receive placebo.

c. Devices to be used

Not applicable

d. Surgical interventions

Not applicable

e. Data to be collected

Please see below for details on data collected and analyses performed.

VI. BIostatistical Analysis

a. Specific data variables being collected

Probabilistic Reward Task (PRT)

The main variable is response bias, which assesses participants' preference for the stimulus paired with more frequent reward, and will be calculated using a published formula ([name] et al 2005). To test the specificity of findings, control analyses will be run on discriminability, which provides a measure of the ability to discriminate the two stimuli. To test **Hypothesis 3a** and **3b**, *Group* (CSA/MDD, CSA/RES, MDD, controls) x *Block* (1,2,3) ANOVAs will be run for response bias and discriminability.

Implicit Learning Serial Reaction Time Task (SRTT)

SRTT data will be analyzed using established procedures (median reaction times for blocks presenting random vs. the predetermined sequence will be calculated; (Kathmann et al, 2005). If group differences emerge in procedural learning, SRTT data will be used as covariates/regressors in all analyses.

Optimism Bias Task

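### The PRT analysis for Hypotheses 3a/3b has no before/after-stress factor, so it can show a group difference under stress but not that stress caused or enlarged it

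*Combined protocol and SAP*

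**What the plan says.** Section II gives the purpose of Aim 3 as "To investigate stress sensitization of the mesocortical system following CSA". Hypothesis 3a expects the CSA/MDD group, relative to controls and CSA/RES, to show lower vmPFC activation and "increased cortisol reactivity following acute stress accompanied by impaired reward learning". Hypothesis 3b expects CSA/RES to resemble controls in reward sensitivity. The aim's own text places these measurements in a reward-learning task done under acute stress.

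Section V.a (ERP Session, EEG Recording) has each participant do the PRT twice, "once before exposure to an acute stressor and once immediately following the stressor". The order around the stressor is fixed; only the stimulus version (mouth or nose) is counterbalanced. The saliva schedule in the same section refers to blocks 1 and 2 of the second PRT, so blocks are subdivisions of a run.

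Section VI.a (Probabilistic Reward Task) names one analysis for Hypotheses 3a and 3b, four groups crossed with Block: "1,2,3) ANOVAs will be run for response bias and discriminability". It contains no stress factor and no change score, and it does not say which run is entered. Section VI.c only refers back to this text.

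**The concern.** A conclusion of stress sensitization needs evidence that a group's reward learning worsens with stress, or worsens more than in other groups. A comparison of groups after the stressor does not supply that if one group already learned less well before it.

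The plan's own background makes such a standing deficit plausible. Section VI.d cites lower response bias in unmedicated MDD than in controls, d = -0.70, and mentions no stressor. If CSA/MDD participants arrive with that deficit, a post-stress difference is likely even when the stressor does nothing, and it could be reported as support for Aim 3. The pre-stress run that could tell the two apart is collected but enters no named comparison with the post-stress run.

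**Working it through.** **The plan's own power figure.** Section VI.d states power above 0.95 for group differences at the behavioral mean d = (0.85 + 0.70 + 1.45)/3 = 1.00. With 23 per group and alpha 0.05, the noncentral t gives 0.955 one-sided and 0.912 two-sided, so the figure reproduces one-sided. It concerns differences between groups. No power is stated for a before/after-stress effect.

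**Inputs for the illustration.**
- From Section VI.d: 23 per group, alpha 0.05, d = 0.70 for the PRT.
- Assumed: two-sided testing; zero stress effect; the 0.70 is a standing deficit in CSA/MDD, equal in both runs and all blocks; CSA/RES equals controls; between-run correlation r from 0.3 to 0.7, because the documents give none.

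**Post-stress run, CSA/MDD vs controls.** Noncentrality = d x sqrt(n/2) = 0.70 x sqrt(11.5) = 2.37 on 44 df. The rejection rate is 0.641 (0.621 with 22 per group after 5% loss).

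**Post-stress run, CSA/MDD vs both controls and CSA/RES.** Hypothesis 3a requires both. Simulation of the four-group, two-run, three-block design (20,000 trials per setting, between-block correlation 0.5 assumed) gives 0.485, 0.489 and 0.483 at r = 0.3, 0.5 and 0.7, or about 49%.

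**Group x Stress contrast (post minus pre).** A constant deficit cancels, so the contrast rejects at its nominal 5%. The simulated omnibus term gives 0.051, 0.049 and 0.052.

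**Group x Block on the post-stress run.** With a deficit constant across blocks it rejects in 0.051, 0.052 and 0.050. This depends on the constancy. A second simulation (4,000 trials, r = 0.5) used a deficit of 0.85 in CSA/MDD and half that in MDD, weighted 0.8, 1.0 and 1.2 over the three blocks:

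| Scenario | Group, post run | Group x Block, post run | Group x Stress |
|---|---|---|---|
| Same deficit before and after stress | 77% | 24% | 5% |
| Deficit only after stress | 76% | 23% | 73% |

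On the post-stress run, the two scenarios are practically indistinguishable by either term of the named analysis.

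**Power of the added contrast.** For an extra post-stress drop of 0.70 SD in CSA/MDD vs controls, the standardized change is 0.70/sqrt(2(1 - r)):
- r = 0.3: 0.592, power 0.50
- r = 0.5: 0.700, power 0.64
- r = 0.7: 0.904, power 0.85

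**Which term should decide.** If that drop is equal across blocks, the simulated omnibus Group x Stress term rejects in 0.496, 0.662 and 0.883, but Group x Stress x Block only in 0.050, 0.048 and 0.050.

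**The case against.** The strongest reply is that the hypothesis makes a claim about level, not change. Aim 3's title concerns the mesocortical system, and reward learning enters Hypothesis 3a as an accompaniment. The rationale in Section I.c speaks of reduced reward responsiveness and "cortisol hypersecretion when exposed to an acute psychosocial stress manipulation". On this reading, a Group test on the post-stress run answers the question asked, and the aim's wording makes that run the natural choice. This stands. A reader might infer that Hypothesis 3a is left without any test; the documents do not support that. What remains is that the run is not named where the analysis is specified, and that a level difference does not establish sensitization.

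Section IV.a does not settle the reading. In prioritizing cell conversion it uses level for CSA/MDD ("greatest impairments in reward learning (as assessed by the PRT) when tested under stress") and change for controls ("greatest resistance against stress-induced reduction in reward learning"), and neither is a hypothesis test.

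A second reply is that the MDD-only group, included "To disentangle CSA- vs. MDD-related effects", guards against misattribution. It does so for abuse versus depression. It does not separate a stress effect from a standing deficit.

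A third is that the source analysis in Section VI.a tests groups or conditions. That may cover before/after stress for vmPFC current density, but not for response bias.

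**Conclusion.** The point holds in limited form. The named PRT analysis can support a statement that CSA/MDD participants learn less well under stress. It cannot support a statement that the impairment arises from, or grows with, stress. Under the stated assumptions, about 49% of trials with no stress effect would show the full Hypothesis 3a pattern in response bias on the post-stress run (64% for the control comparison alone), against about 5% for Group x Stress.

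These percentages are not error rates of the plan. They carry a single MDD-versus-control estimate over to CSA/MDD as a stress-independent deficit, which the documents do not establish. They show only how readily a standing deficit could pass for sensitization. Nor is Group x Block safe in general: it stays near 5% only for a deficit that is constant across blocks.

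A reader might extend the point to the whole of Aim 3. The vmPFC source test may already cover conditions. The absence of a named test for the five cortisol samples is a separate matter, and the unnamed run for the FRN is missing detail. Neither is part of this point.

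This should be fixed; it does not invalidate the study, because the paired data are collected.

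**What to change.** - Name the post-stress run as the one used for the level claim in Hypotheses 3a and 3b, and keep the Group test on it.
- Add Stress (pre, post) as a within-subject factor, giving Group x Stress x Block for response bias and discriminability.
- Make the Group x Stress contrasts (CSA/MDD vs controls, CSA/MDD vs CSA/RES, CSA/RES vs controls) the test for any claim of stress-related change in reward learning. State that Group x Stress decides, not the three-way term.

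**Cost.** No new measurements, but three limits should be stated:
1. Power of the change contrast is modest: 0.50 to 0.85 over the assumed correlations for an extra 0.70 SD drop. It would be lower if fewer than 23 per group have both runs.
2. There is no unstressed repeat, so the result is change across the stressor. If groups differed by an assumed 0.3 SD in practice or fatigue, the contrast would be significant in 13%, 17% and 25% of trials at r = 0.3, 0.5 and 0.7.
3. Section V.a (Randomization) records that the blind was broken in May 2016 for preliminary analyses, and Appendix 2 reports interim PET results. The documents do not say whether PRT data were examined. The change must be dated, and labelled post hoc if they were.

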Specific Aim 1: To investigate that increased DA transmission normalizes reward responsiveness and optimism in females with histories of CSA. We will use reward paradigms from our pilot work in conjunction with a pharmacological challenge to test that decreased phasic DA transmission within mesolimbic regions plays a key role in CSA sequelae. We hypothesize that increased phasic DA release – achieved through presynaptic DA autoreceptor blocking by means of single low dose of the D₂/D₃ antagonist amisulpride – will improve positive reinforcement learning and boost activation in reward-related brain regions, particularly the ventral and dorsal striatum (**Hypothesis 1a**). Due to hypothesized downregulation of mesolimbic DA pathways, we expect that individuals with CSA and current MDD (“CSA/MDD”) will show the largest improvements. Confirming that a well-functioning reward system is a marker of resilience, adults with CSA without lifetime psychopathology (“CSA/RES”) will show normative activation and performance under placebo (**Hypothesis 1b**). We also hypothesize that increased phasic DA release – achieved through amisulpride – will re-orient MDD individuals from a pessimistic outlook to an optimistic outlook as measured by the Optimism Bias Task (**Hypothesis 1c**). In addition, under placebo, MDD participants will show a pessimistic outlook as compared with healthy controls (**Hypothesis 1d**).

Specific Aim 2: To investigate dopamine transporter and its relation to reward processing in females with CSA history. We will utilize positron emission tomography (PET) and a highly selective radioactive ligand (¹¹C-altropane) to assess DAT binding in CSA adults. Animal studies have shown that early adversity leads to DAT downregulation within mesolimbic regions. In humans, we have observed links between altropane binding and depressive symptoms, the most common CSA sequelae). Based on our data, we expect that, relative to control and CSA/RES subjects, CSA/MDD adults will show reduced altropane binding (**Hypothesis 2a**). We further hypothesize that, among the CSA/MDD group, reduced DAT will correlate with blunted reinforcement learning and striatal activation (**Hypothesis 2b**).

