This task is a belief updating task. On each trial participants are presented with a description of 40 different adverse life events (e.g. Alzheimer's disease, robbery). They are asked to provide estimates of their likelihood of experiencing these events in their lifetime. After each trial, participants are presented with the average probability of that event occurring to a person from the same sociocultural environment. We then ask participants to estimate their likelihoods for the same 40 events again in a second session to examine how they incorporate the information into their estimates. To control for potential confounds participants complete a memory test for the information presented and rate all stimuli on emotional arousal, negativity and past experience. The task takes approximately 30 minutes to complete.

Skin Fibroblast Component

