For each trial we compare the extent to which participants altered their estimates in response to the information presented (update score = second estimate- first estimate). We then compare these scores for trials in which participants receive good news (trials where the actuarial probability of a negative event is less than participants' estimate of their likelihood) with trials in which they receive bad news trials (where the actuarial probability of a negative event is greater than participants estimate of their likelihood).

Self-Concept Attention Task

Reaction time (RT) and responses to trait words are compared between the accompanying image types (self, other person, or scrambled).

Scalp ERP and Source Analyses

ERP analyses will follow prior work ([name] et al 2002, 2003). ERPs will be collected during the Probabilistic Reward Task. Briefly, ERPs will be computed covering 1024 ms and time-locked to the onset of the stimulus (Rich, Lean) and feedback using a 100-ms pre-stimulus baseline. Analyses will focus on the feedback-related negativity (FRN). The FRN (measured as the most negative deflection 200-400ms after reward feedback over fronto-central electrodes) is hypothesized to reflect phasic DA reward prediction signals projecting from the basal ganglia to the ACC and used to guide behavior according to reinforcements (Holroyd & Coles 2002). Studies in the PI's lab have shown that reduced reinforcement learning is linked to a larger (i.e., more negative) FRN, likely due to a reliance on external feedback to guide behavior (Bogdan et al 2011; Santesso et al 2008, 2009). Thus, relative to controls, the CSA/MDD – but not CSA/RES group – will show larger FRN and reduced OFC and vmPFC activation to reward feedback. *Group x Electrode* (AFz, Fz, FCz, Cz) ANOVAs will be conducted on FRN amplitude and latency. As in prior work (Bogdan et al 2011; Santesso et al 2008), intracortical current density will be computed at the time of the FRN using LORETA (Pascual-Marqui et al 1999). Whole-brain voxelwise tests will test differences between groups or conditions. To control for Type I error, permutation procedures will be used to calculate the false-positive rate under the Null Hypothesis (Nichols & Holmes 2002).

Amisulpride Behavioral Analyses for PSST and MID

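### The Optimism Bias score is signed the same way on good-news and bad-news trials, so the written contrast measures total updating and does not isolate the bias that Hypotheses 1c and 1d are about

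*Combined protocol and SAP*

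**What the plan says.** The scoring rule is in Section VI.a under Optimism Bias Task. It opens with "For each trial we compare the extent to which participants altered their estimates" and defines the score in parentheses as "update score = second estimate- first estimate". The next step is "We then compare these scores for trials in which participants receive good news" against trials with bad news. Good-news trials are "trials where the actuarial probability of a negative event is less than participants' estimate of their likelihood"; bad-news trials are those "where the actuarial probability of a negative event is greater than participants estimate of their likelihood".

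The task description in Section V.a (PET Session) says that "participants are presented with a description of 40 different adverse life events", so a lower estimate is the optimistic direction throughout. First and second estimates are both collected. No scoring is given there.

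Section II.a (Specific Aim 1) attaches two hypotheses to the outcome. Hypothesis 1c is that amisulpride "will re-orient MDD individuals from a pessimistic outlook to an optimistic outlook as measured by the Optimism Bias Task". Hypothesis 1d is that "under placebo, MDD participants will show a pessimistic outlook as compared with healthy controls".

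Nothing else completes the rule. Section VI.b lists no endpoints, VI.c refers back to VI.a, and VI.d gives no effect size for this task. The entries for the probabilistic reward task and the serial reaction time task point to published or established scoring; this entry does not. No Group or Drug term is written for it.

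**The concern.** Optimism bias in a belief-updating task is an asymmetry: larger updating after good news than after bad news. A raw second-minus-first score changes sign with the type of news, so setting the two trial types against each other adds the two update sizes when the hypotheses need their difference.

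Followed literally, the rule has two consequences for Hypotheses 1c and 1d. A real shift in bias that leaves total updating unchanged goes unseen. A group or drug difference in general responsiveness to information, with no bias at all, appears as a difference on the optimism measure.

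The direction of the score should not be left to the analyst. The Randomization text in Section V.a records that the blind was broken in May 2016 for preliminary analyses, and sets a further break for November 2016.

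**Working it through.** The plan states no figure for this task, so there is none to reproduce. The main result is algebra and needs no assumed data.

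**1. Algebra.** Let G and B be a participant's mean movement toward the information on good-news and bad-news trials.
- Good news: the actuarial risk is below the first estimate, so second minus first = -G.
- Bad news: the actuarial risk is above the first estimate, so second minus first = +B.
- Written contrast, good minus bad: (-G) - (+B) = -(G+B).
- Quantity needed: G-B.

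**2. Three profiles (points, chosen for illustration).**

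| Profile | G | B | Written, -(G+B) | Direction-coded, G-B |
|---|---|---|---|---|
| Optimistic | 15 | 5 | -20 | +10 |
| Unbiased | 10 | 10 | -20 | 0 |
| Pessimistic | 5 | 15 | -20 | -10 |

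**3. Group comparisons.** The documents give no means or SDs. Assumed: a 20-point gap between estimate and actuarial risk, updating rates as listed (so G or B = 20 x rate), between-participant SD of each rate 0.12, trial noise SD 10, 20 trials of each type, G and B independent, two-sided alpha 0.05. The SD of either contrast is sqrt(2 x ((20 x 0.12)^2 + 10^2/20)) = sqrt(2 x (5.76 + 5)) = 4.64 points. A 4-point difference is therefore 4/4.64 = 0.86 SD.

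Rates are good/bad. Differences are second group minus first.

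| Comparison | Written scores | Difference | Direction-coded scores | Difference |
|---|---|---|---|---|
| Equal total: 0.4/0.2 v 0.3/0.3 | -12 v -12 | 0 | +4 v 0 | -4 |
| Good-news drop only: 0.4/0.2 v 0.2/0.2 | -12 v -8 | +4 | +4 v 0 | -4 |
| Bad-news rise only: 0.4/0.2 v 0.4/0.4 | -12 v -16 | -4 | +4 v 0 | -4 |
| No bias, total differs: 0.3/0.3 v 0.2/0.2 | -12 v -8 | +4 | 0 v 0 | 0 |

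In the first three rows the second group has lost the same 4 points of optimism. The written score shows no change, a rise and a fall.

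**4. Sample size for Hypothesis 1d.** It is tested under placebo, and half of each group of 23 gets placebo: 23/2 = 11.5, so 11 or 12 per group. Simulated rejection rates (20,000 runs):

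| Comparison | 12 v 11: written | 12 v 11: direction-coded | 23 v 23: written | 23 v 23: direction-coded |
|---|---|---|---|---|
| Equal total | 5% | about 50% | 5% | about 81% |
| One trial type only | about 50% | about 50% | about 81% | about 81% |
| No bias, total differs | about 50% (false) | 5% | about 81% (false) | 5% |

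The 23 v 23 columns would apply only if both drug arms were pooled, which Hypothesis 1d does not do.

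**The case against.** **Extent suggests size.** The sentence holding the formula speaks of the extent of change, so magnitudes may have been meant and the parenthesis may be loose drafting. That is plausible, and it limits any claim about what the analysts will actually do. It does not repair the rule: the formula is explicit, and no absolute value or sign reversal is written. A plain absolute value would also count movement away from the information as updating.

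**The contrast is not blind to bias.** A reader might infer that the written score can never register a group difference in optimism. The documents do not support that. Where only one trial type differs, the written and direction-coded scores have the same power. What stands is narrower: the direction of the result is uninterpretable, and it is mixed with overall updating.

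**The subtraction is inferred.** The plan says only that the scores are compared. In a Group by news-type model on the raw scores, the Group main effect (the mean over the two types) is (B-G)/2, which does carry the bias. That is correct, but the plan does not specify that test; the comparison it writes is between news types.

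**An unbiased group would look biased.** Under the written rule, a within-group good-versus-bad test in unbiased participants is significant in essentially every simulated run. A reader might take this as the false-positive rate for the hypotheses. It is not: 1d compares groups and 1c is a drug effect.

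**Recoding alone may not rescue 1c.** Section V.a places this task before the PET scan, whereas amisulpride is given in the fMRI session. That is a separate question, and correct scoring does not answer it.

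**Conclusion.** The point holds for the rule as written. The good-versus-bad contrast equals -(G+B) and does not isolate G-B. It gives one value to optimistic, unbiased and pessimistic profiles with equal total updating, moves when groups differ only in overall updating, and has a sign that depends on which trial type changed.

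This rests on the signed formula and on the plan's own definitions of good and bad news. The percentages rest on the assumed rates and SDs and are illustrations only: with equal total updating at 12 v 11, about 5% as written against about 50% recoded. Even correctly scored, Hypothesis 1d would have modest power under those assumptions.

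Two stronger readings should be avoided. One is that the data are compromised: both estimates are recorded, so any score can be rebuilt. The other is that the trial's analysis is known to have used the wrong quantity: the documents show only what was written, and the wording leaves room for a slip.

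**What to change.** In Section VI.a, replace the single formula with a direction-coded one:
- good-news trials: first estimate minus second estimate;
- bad-news trials: second estimate minus first estimate;
- optimism bias: mean good-news update minus mean bad-news update, positive meaning optimistic.

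Then name the tests on that quantity. For Hypothesis 1d, compare MDD participants with controls among those on placebo (the Group by news-type interaction on direction-coded scores), and say whether the CSA/MDD and MDD groups are pooled. For Hypothesis 1c, compare amisulpride with placebo among MDD participants (the Drug by news-type interaction). Total updating, G+B, can be reported beside it as a separate descriptive measure.

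Date the change, and state whether anyone making it had seen unblinded results for this task. The cost is a line of wording for the score, a sentence for the tests, and a recode of estimates the task already records. No new data are needed.
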